Participants and study staff assessing outcomes will be blinded to intervention status. Research assistants on the study staff will add the sleep education handouts with video links to discharge instructions to be delivered by the bedside nurse in concurrence with clinical care. The intervention was designed this way to increase feasibility and generalizability for the future by providing a means of information dissemination that could be easily and widely adopted if effective within different health systems in conjunction with clinical care. This research assistant will be notified by REDCap when a participant is enrolled, and will place instructions in the discharge section of the electronic health record that is automatically printed at discharge, without interaction with other study team members or families. Additionally, this portion of the intervention will be delivered at hospital discharge concurrent with clinical care to improve generalizability in future work by limiting change to institutional care practices. The sleep handout will be delivered in conjunction with standard discharge instructions provided to all TBI patients and other care will remain per our institutional TBI standards directed by the

patient's care team (an example of these standard TBI discharge instructions are uploaded in supporting documentation).

Outcomes: We will include measures of feasibility, acceptability, and effectiveness. See **Table 1** for summary of outcomes and schedule of collection. Outcomes will be assessed at hospital discharge, and a study visit at 30 days \pm 17 days. 30-day outcomes assessments will be defined from the time of study intervention initiation. The primary outcomes will be measures of feasibility and acceptability, with exploration of effectiveness in this pilot trial. Quantitative measures of recruitment and retention (feasibility), adverse events and utilization (acceptability), and total score of the Sleep Disturbances Scale for Children (SDSC) at 30-days (clinical effectiveness) will be used. Outcomes will be collected by the study team over the phone, via chart review, or via electronic survey administered through REDCap. Secondary and other outcome measures will be collected by activity monitor, chart review, survey, sleep questionnaire, and actigraphy devices. Fitbits will be worn continuously during the 30 day study period except when removed for charging the device.

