	
adherent if device worn for ≥5 nights consecutively; we will assess sleep routines through actigraphy; will be counted as unknown if did not participate in the actigraphy portion
 
Quantitative survey: "How many nights each week did you take the study medication since discharge?"
 
None, 1-3, 3-4, 5-7, All
 
Quantitative survey response: "Did you receive sleep education with your hospital discharge paperwork?"; choices of a) did not receive discharge paperwork; b) I did not receive any sleep education at discharge; c) I received it, but did not use it; d) I received it, but did not find it helpful; e) I received it, and found it helpful; responses to this question will also be compared with the discharge instructions within the electronic health record to determine if the resource was provided as intended.
	Descriptive percent; Chi-square to compare intervention arms
Acceptability Outcomes		
*Adverse Events (discharge, 30-day)	
Qualitative response to survey: "Did you have any new medical problems since the last study visit?"
 
Quantitative yes/no response: "Did you have any of the following symptoms since the last visit"
 
 a. Nausea b. Vomiting c. Diarrhea d. Drowsiness e. Fatigue f. Headache g. Behavioral changes h. Vivid dreams i. Nightmares j. Waking up at night k. Itchy skin l. Rash m. Appetite changes n. Bodily pain or aches o. Chest pain p. Enuresis or bedwetting q. Dizziness r. Tinnitus or ringing in the ears s. Feeling cold 
Evaluation of medical record, patient assessments to quantify adverse events and unexpected problems collected as a dichotomized yes/no and number of events
	
Thematic analysis
 
Descriptive percent and mean with standard deviation; Chi-square (yes/no) and Mann-Whitney U test (continuous) to compare intervention arms

Satisfaction (30-day)	Quantitative rankings on a likert scale survey: experiences with the study overall, consent process, study team, study intervention, questionnaires, Actigraphy devices, care received	Descriptive median and interquartile range; Mann-Whitney U tests

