	
clinically in the hospital, care received clinically after hospital discharge
 
Qualitative response to survey: "If you were provided sleep education, and did not use it or find it helpful, please describe reasons:"; "If you were provided sleep education, and found it helpful, please describe how you utilized the resources"; "How can the study team improve the experience of participants in future studies"
	
to compare intervention arms
 
Thematic analysis

Reasons for Non-adherence (30-day)	Qualitative responses to survey: "Please describe reasons for not taking the study medication"; "Please describe reasons for not using the sleep educational resources provided at hospital discharge"; "How could the study team improve the design of the study in the future"; "How could the study be improved in the future"	Thematic analysis
Exploratory Clinical Effectiveness Outcomes		
*Sleep wake disturbance (Baseline, 30-day)	Sleep Disturbances Scale for Children (SDSC) total score	Descriptive mean and standard deviation; linear regression to compare intervention arms
Sleep wake disturbance phenotypes (Baseline, 30-day)	SDSC subscale scores, Children's Chronotype Questionnaire, actigraphy measures (total sleep time, sleep onset latency, wake after sleep onset, sleep efficiency, night sleep:total sleep time, sleep onset, sleep offset, daytime sleep episodes, duration of daytime sleep)	Descriptive mean and standard deviation; linear regression to compare intervention arms
Global health (Baseline, 30-day)	Pediatric Quality of Life Inventory (PedsQL) scales for core, fatigue	Descriptive mean and standard deviation; linear regression to compare intervention arms
Emotional health (Baseline, 30-day)	PROMIS measures for anxiety and depression	Descriptive mean and standard deviation; linear regression to compare intervention arms
Physical function (Baseline, 30-day)	PROMIS measures for pain; Functional Status Scale	Descriptive mean and standard deviation; linear regression to compare intervention arms
Cognitive function (Baseline, 30-day)	Behavior Rating Inventory of Executive Function, Second Edition	Descriptive mean and standard deviation; linear regression to compare intervention arms

*Primary outcomes

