a. Sharing of Results with Subjects

Data from this clinical trial will not be shared directly with participants. The results of the clinical trial and de-identified data will be made in accordance with NIH regulations and clinicaltrials.gov.

b. Data and Specimen Banking

No specimens will be stored. Study records will be retained for the longest regulatory retention period. After that time, records will be destroyed in a confidential manner.

8. Data Analysis

See Table 1 for outline of data analysis planned for study outcomes. As this is a pilot intervention trial, the focus will be on feasibility and acceptability of the pragmatic intervention trial. We will also explore effectiveness outcomes, but recognized we will be underpowered for a definitive effectiveness trial within this heterogeneous population selected to be representative of the population of interest. We will use our pilot trial to inform a future larger trial that will include longitudinal real world health outcomes relevant to the pediatric TBI population if supported by our preliminary results.

Prior to evaluating outcomes, we will perform a thorough descriptive analysis of participant baseline characteristics (age, race, ethnicity, gender, pre-injury comorbidities, TBI characteristics including severity, location, and type). We will examine patterns of missingness in our outcomes collected at 1-month, differences in participant and non-participant characteristics, and differences in participants who completed versus dropped out of the study to ascertain potential bias. Additionally, we will describe and compare the distribution of patient and clinical characteristics, including age and TBI severity, across treatment groups to ensure our randomization protocol was successful. Comparisons between groups will be made using chi-square tests for categorical variables. Depending on characteristics of the data, t-tests and Mann-Whitney U tests will be used to compare continuous variables between groups. We plan to perform both intention to treat and per protocol analyses.

Quantitative feasibility outcomes will be presented as a percentage of patients, the denominators of which are listed in Table 1. Comparisons between groups will be made with chi-square tests.

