Quantitative acceptability outcomes for adverse events will be dichotomized to yes/no and evaluated as a total number for each patient summarized using percent and median with interquartile range (IQR), respectively. Acceptability outcomes for satisfaction will be measured using Likert scales for which we will present results as medians and IQR. Chi-square tests will be used to compare dichotomized outcomes between treatment groups, and Mann-Whitney U tests will be used to compare total number of events. Effectiveness outcomes will be summarized using means and standard deviations, except for daytime sleep episodes which will be summarized as a median and IQR; these outcomes will be summarized for the overall study population and by treatment group. We will primarily examine the effectiveness of our intervention using linear regression to assess differences in the total SDSC score across treatment groups at 1-month. Linear regression will allow us to assess differences in effectiveness outcomes while controlling for covariates that may confound this relationship; covariates of particular interest will include age and TBI characteristics. Covariates identified in our initial descriptive analysis as significantly different between treatment groups, and covariates significantly associated with SDSC total score in bivariate analyses will also be explored with multiple linear regression.

Secondary effectiveness outcomes that specifically evaluate sleep phenotypes (measured by questionnaire and actigraphy) will be similarly evaluated with linear regression, except daytime sleep episodes which will be modeled using a count model, such as Poisson or negative binomial regression. For these secondary effectiveness outcomes, our focus is the magnitude of the association rather than statistical significance, as multiple comparisons will be made. Our primary goal with this secondary analysis will be to determine if the intervention appears effective for particular phenotypes that could be targeted in future studies. Results of these secondary analyses will be used as estimates for effect sizes in future intervention study design.

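### Daytime sleep episodes: Table 1 should be brought into line with Section 8, and the count model needs an exposure term for days of device wear

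*Combined protocol and SAP*

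**What the plan says.** Section 8 (Data Analysis) makes two explicit exceptions for this variable. Descriptively, effectiveness outcomes get means and SDs "except for daytime sleep episodes which will be summarized as a median and IQR". For the comparison of arms, the sleep-phenotype outcomes get linear regression, "except daytime sleep episodes which will be modeled using a count model, such as Poisson or negative binomial regression".

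Table 1 (Section 6) lists the variable in the sleep wake disturbance phenotypes row, among "sleep onset, sleep offset, daytime sleep episodes, duration of daytime sleep". The analysis column for that whole row reads "Descriptive mean and standard deviation; linear regression to compare intervention arms", with no exception. Section 8 opens by sending the reader to that table: "See Table 1 for outline of data analysis planned for study outcomes".

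On wear, Section 6 says "Fitbits will be worn continuously during the 30 day study period except when removed for charging the device". The only wear threshold is in the adherence row of Table 1, where actigraphy counts as "adherent if device worn for ≥5 nights consecutively". Sections 7 and 11a let participants take the device off or leave this part of the study. Section 11a has devices given out at clinical visits or mailed. Section 7 relies on participants syncing at least weekly.

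No section gives an offset, a rate per day, a minimum number of valid days for analysis, or the window over which episodes are counted.

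**The concern.** There are two separate gaps.

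First, an analyst working from Table 1 would fit a linear model and report a mean and SD. One working from Section 8 would fit a count model and report a median and IQR. Section 8 also leaves the choice between Poisson and negative binomial open.

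Second, a count means little without the time over which it was collected. A child observed for longer has more opportunity to record naps. If the outcome is a total over the days worn, the model mixes napping with wear time. The same applies to a raw median and IQR.

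Section 8 says the secondary outcomes are to be read for the size of the association rather than for significance, and that the results will supply effect sizes for later trials. The size of the association is what an unmodelled exposure distorts or blurs.

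**Working it through.** The plan gives no nap rate, wear distribution or power figure for this outcome, so there is no stated number to reproduce.

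**Inputs from the documents.** Planned wear is 30 days (Section 6). Five consecutive nights is the adherence label (Table 1). Total enrolment is 30 to 50 at 1:1 (Section 5a), so 15 to 25 per arm.

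**Assumptions, not in the documents.** The rate is 0.2 episodes per day (range 0.1 to 0.5). Wear is uniform over whole days in the ranges shown. Overdispersion between children is 0 or 0.5. There is no true effect. Tests are two-sided at 0.05.

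**Step 1: expected ratio of total counts without an offset.** Expected count = rate × days worn, so

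expected count ratio = true rate ratio × ratio of mean days worn.

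- Two children with the same nap rate, worn 30 and 5 days: 30/5 = 6-fold difference.
- Two arms with the same nap rate, mean wear 25 and 20 days: 20/25 = 0.80.
- Mean wear 25 and 15 days: 15/25 = 0.60.

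**Step 2: same wide wear distribution in both arms (5 to 30 days), 15 per arm.**

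- Mean wear is 17.5 days, variance (26² − 1)/12 = 56.25, SD 7.5, coefficient of variation 7.5/17.5 = 0.429.
- SD of the log ratio of mean wear ≈ √(2/15) × 0.429 = 0.157 (0.121 at 25 per arm).
- Expected count per arm is 15 × 0.2 × 17.5 = 52.5, so the Poisson standard error is √(2/52.5) = 0.195.
- Actual SD of the log ratio without an offset ≈ √(0.195² + 0.157²) = 0.250.
- The test still divides by 0.195, so it rejects when |Z| > 1.96 × 0.195/0.250 = 1.53, a probability of about 12.6%.

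There is no systematic bias here, only extra noise that the Poisson model does not see.

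**Step 3: same narrow wear distribution in both arms (20 to 30 days), 15 per arm.** Mean wear is 25, variance (11² − 1)/12 = 10, SD 3.16, coefficient of variation 0.126. The SD of the log wear ratio is √(2/15) × 0.126 = 0.046. The Poisson standard error is √(2/75) = 0.163, and the actual SD is √(0.163² + 0.046²) = 0.170. The rejection rate is about 6%, so the inflation has nearly gone.

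**Step 4: simulation, Poisson model, 5,000 trials per setting, no overdispersion.** Ranges run over rates of 0.1 to 0.5 per day.

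| Wear, days | Per arm | Ratio, no offset | Rejects, no offset | Rejects, with offset |
|---|---|---|---|---|
| 5–30 in both arms | 15 | 0.995–1.008 | 8%–23% | 4.2%–5.5% |
| 5–30 in both arms | 25 | 0.996–0.998 | 8%–22% | 4.7%–5.1% |
| 20–30 v 10–30 | 15 | 0.795–0.798 | 17%–53% | 5.0% |
| 20–30 v 10–30 | 25 | 0.797–0.800 | 22%–70% | 4.5%–4.9% |

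With 5 to 30 days in both arms at 0.2 per day, the no-offset rejection rate is 11.5% at 15 per arm and 13.2% at 25, which agrees with Step 2. At 15 per arm the offset cuts the SD of the log ratio from 0.253 to 0.194. With the offset, the ratio is between 0.995 and 1.004 in every setting.

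**Step 5: which count model.** With overdispersion of 0.5 and wear of 5 to 30 days in both arms, Poisson with the offset still rejects in roughly 24% to 30% of null trials. Negative binomial with the offset rejects in 5% to 7%. Negative binomial without the offset is close to nominal when wear is alike in the arms (5.0% to 7.5%), but it does not remove bias when wear differs. The offset and a model that allows overdispersion solve different problems.

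**The case against.** **The conflict resolves itself.** Section 8 words its rule as an exception, twice, and calls Table 1 an outline. The Table 1 row covers about a dozen measures and states their default. This stands: the intended analysis is clear, and the Table 1 correction is editorial.

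**The outcome may not be a total count.** The plan never defines it, so a fixed window or a daily count is possible, and naming a count model without its offset does not exclude one. This also stands. The gap is an undefined variable and an unstated exposure term, not a demonstrated wrong model.

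**Wear of 5 to 30 days is not documented.** A reader might infer that range by setting the adherence threshold against the planned 30 days. The documents do not support it. Five nights is an adherence label, not a floor for analysis. It counts nights, whereas naps need daytime wear, and actual wear could be lower. Continuous wear is intended, and reminders to sync and charge are planned.

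**Bias needs unequal wear by arm.** A reader might infer that wear differences will show up as a false treatment effect. One scenario, 18 to 30 days in one arm against 5 to 30 in the other at 20 per arm, gives a ratio of 0.72 and about 52% false positives. Section 6 blinds participants and outcome assessors and gives both arms the sleep handout. Nothing in the documents says that wear is expected to differ. Those figures show what unequal wear could do; they are not an expected result.

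**Type I error is a secondary yardstick.** Section 8 looks to magnitude, and negative binomial is already among its options. With similar wear, choosing it removes most of the inflation. That is fair, but the point estimate remains noisier than it need be, and unprotected if wear does differ.

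**Conclusion.** The point holds as a modest, inexpensive improvement to a secondary exploratory outcome. Two statements rest on the text alone: Table 1 and Section 8 differ, and no exposure term or counting window is given although wear can vary between children.

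The size of the effect rests on assumptions. If episodes are totalled over days worn, the expected ratio with no true effect equals the ratio of mean wear, for example 0.80 at 25 against 20 days. If wear is alike in the two arms there is no systematic bias. The cost is then extra noise (SD of the log ratio about 0.25 instead of 0.19 at 15 per arm, with wear of 5 to 30 days) and, under plain Poisson, a false-positive rate of about 12% to 13% at 0.2 episodes per day. That falls to about 6% if all children wear the device for 20 to 30 days.

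The stronger conclusion, that differences in wear will be reported as differences in napping, is not supported. It would need both a total-count outcome and a difference in mean wear between blinded arms, and the documents establish neither.

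**What to change.** 1. In Table 1, take daytime sleep episodes out of the linear-regression row, or add the exception, so that it matches Section 8.
2. In both places, name one model: negative binomial regression, or Poisson with robust standard errors, with offset log(valid wear days).
3. Define a valid day in terms of daytime wear, the window over which episodes are counted, and any minimum number of valid days for inclusion. Keep this separate from the five-night adherence label.
4. Summarise the outcome as episodes per valid day, with median and IQR.
5. Report valid wear days by arm, so that a reader can see whether exposure was balanced.

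The cost is a few lines of wording and one derived variable. Section 7 describes exportable activity and sleep data but names no ready-made count of valid wear days, so that variable must be defined and computed from the Fitbit data, preferably before unblinding. Nothing in recruitment, visits or data collection changes.

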We expect to enroll between 30-50 patients based on eligibility over 2.5 years of recruitment. This estimate is based on the most recent hospital admissions data since the start of the COVID-19 pandemic estimating approximately 100 patients will qualify for the study over 2.5 years. Participants will be randomized 1:1 to receive the intervention. Recruitment and retention will be assessed during the trial as outcomes.

b. Inclusion and Exclusion Criteria

Children \geq 6 years and <19 years of age admitted with TBI (defined as injury to the head from external forces with severity mild, moderate, or severe classified by Glasgow Coma Scale) will be included.

Children under the age of 6 years will be excluded due to increased variability in baseline sleep patterns, daytime napping, and lack of standardized tools identifying sleep outcomes between children younger and older than 6 years. Patients over age 18 years will be excluded as they are primarily treated in adult care units and the study focus is pediatric. Patients unable to tolerate enteral medications within 72 hours of hospital admission, as defined by the clinical care Attending Physician, will be excluded from the study. Patients undergoing dialysis, requiring extracorporeal life support, or with significant liver dysfunction (defined as aspartate aminotransferase (AST) or alanine aminotransferase (ALT) more than 2 times the upper limit of normal for age) will be excluded. Patients about whom the Attending Physician has any safety

concerns regarding use of melatonin as per clinical judgement will be excluded from the study. Patients with abusive trauma will be excluded. Suspected or known prisoners are excluded. Pregnant patients are excluded. There will be no requirement for contraception during the trial in female patients of child-bearing age. Patients must have a parent or guardian with whom they reside in order to participate in the study given the parent-reported measures used for outcomes.

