Screening: Children with traumatic brain injury (TBI) will be screened for inclusion in the study by the Trauma Research Group (TRG) on admission to Oregon Health and Science University or Doernbecher Children's Hospital. Research coordinators with the TRG are available to screen all TBI admissions for inclusion into active research studies 24 hours per day. Screening activities will take place under a HIPAA waiver per the "Activities Preparatory to Research" policy at OHSU. Given the extensive experience and training of the TRG, we expect very few if any screen failures of TBI admissions, and this will be actively monitored throughout the study period.

Recruitment Procedures: Recruitment will be maximized by using consistent trained staff within the TRG that have extensive experience consenting subjects and surrogates for research, including critically injured children. The recruitment process will be overseen by [name], a Pediatric Critical Care physician, with expertise in caring for critically injured children. TRG staff

are trained and mindful of the critical nature of traumatic brain injury and will ensure the appropriate time and conditions for obtaining informed consent. Individual staff are monitored to ensure adherence to TRG standard operating procedures and study protocols.

The appropriate time to approach patients will be determined by study staff and clinical care staff, and consent will be obtained within 72 hours of Pediatric Intensive Care Unit admission to ensure starting the intervention as early as possible. Delaying consent for critically ill patients will not adversely affect the study outcomes, but will allow for acute stabilization of patients prior to consideration of study inclusion, ensure ability to administer enteral medications, and to allow for determination by the primary clinical care team of a patient's likelihood of survival. Consent procedures will be reviewed at least quarterly during TRG coordinator meetings to ensure ongoing consistency. The minimum goal set for recruitment is 50% of eligible patients.

Retention: All patients consenting for inclusion will have phone, address, email contact information collected at time of consent. Outcomes will be obtained at 1-month follow-up as described.

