Text messaging will be used for system generated reminder prompts such as "Please sync your device"; or if battery is low, "Please charge your battery" during the 1-month study period while participants wear the Fitbit. Text messaging functions require sharing of participant phone numbers with the Fitabase platform and Twilio, Inc.

Feasibility benchmarks will be assessed every 6 months during the trial. If feasibility benchmarks are not met, study procedures and the protocol will be reviewed using input from stakeholders and preliminary data to determine if changes are warranted.

Table 1. Outcomes Evaluation and Analysis for Melatonin Trial

Outcome (time collected)	Measurement or Assessment Tool	Analysis
Feasibility Outcomes		
*Recruitment (6-monthly feasibility reviews)	Number subjects consented/approached; goal >50%	Descriptive percent
*Retention (6-monthly feasibility reviews)	Quantitative Number completed/consented; Goal >90%	Descriptive percent
Screen failure (6-monthly feasibility reviews)	Number approached/eligible patients; expect <<5%; eligible patients will be derived from the OHSU Trauma Registry and compared to study logs	Descriptive percent
Reasons for Participation/ Non-participation (time of approach/consent)	Qualitative response to survey: "Please describe reasons you chose [not to or to] participate in this research study"; "Could the study team do something different in the future to increase chances you would participate in future studies?"	Thematic analysis
Reasons for drop-out (30-day)	Qualitative response to survey: "We would like to know how we can improve our study in the future. Please tell us your reasons for leaving the trial"; "How could the study team have assisted you better in completing the trial?"	Thematic analysis
Adherence (30-day)	Pill counts: adherent if \geq 75% prescribed pills are taken at the follow-up study visit; will be counted as unknown if pill count not available Sleep tracking usage: actigraphy data and sleep diaries will be compared to age based recommendations; actigraphy counted as	Descriptive percent; Chi-square to compare intervention arms Descriptive percent; Chi-square to compare intervention arms

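### Section 8 turns raw phenotype effects, screened by size in 30-50 children, into effect sizes for the next trial, with no allowance for selection or imprecision

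*Combined protocol and SAP*

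**What the plan says.** The relevant text is the paragraph on secondary effectiveness outcomes in section 8 (Data Analysis). Phenotype outcomes from questionnaires and actigraphy are to be modelled by linear regression, with a count model for daytime sleep episodes. Three statements follow in turn:

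- On how results are read: "our focus is the magnitude of the association rather than statistical significance, as multiple comparisons will be made".
- On the aim, which is to "determine if the intervention appears effective for particular phenotypes that could be targeted in future studies".
- On their use: "Results of these secondary analyses will be used as estimates for effect sizes in future intervention study design".

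Table 1 (section 6) lists the outcomes: nine actigraphy measures, a chronotype questionnaire and the SDSC subscales, whose number is not given. Its analysis column names means, standard deviations and linear regression. Neither place mentions confidence intervals, shrinkage, a minimum important difference or a rule for choosing among phenotypes.

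On size, section 5a says: "We expect to enroll between 30-50 patients based on eligibility over 2.5 years of recruitment". Section 8 concedes that the pilot is underpowered for effectiveness. SDSC total score is the main effectiveness outcome.

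**The concern.** Reading results by magnitude does not avoid the multiplicity problem. When many noisy estimates are compared and attention goes to those that look large, the ones singled out are on average overestimates, whether or not a p-value is computed. The plan then takes effect sizes for future design from the same data.

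Sections 2, 4 and 8 all present informing a larger trial as a purpose of this pilot, so an effect size handed to that trial is one of its products. An inflated value would lead to a next trial too small to detect the real effect.

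**Working it through.** **Inputs from the documents.** Section 5a gives 30-50 children and 1:1 allocation ("Participants will be randomized 1:1 to receive the intervention"), so 15-25 per arm. The plan's only sample-size figure is an accrual estimate. Its upper end reproduces from section 5a ("estimating approximately 100 patients will qualify for the study over 2.5 years") and section 5e ("The minimum goal set for recruitment is 50% of eligible patients"): 100 x 0.50 = 50. No derivation is given for 30. Table 1 sets the retention target ("Quantitative Number completed/consented; Goal >90" per cent). At 90%, 30 x 0.9 / 2 = 13.5 and 50 x 0.9 / 2 = 22.5 are analysed per arm. The number of outcomes is at least 9 + 1 = 10.

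**Assumptions, because the documents are silent.** Standardised effects with SD 1 and a normal approximation; equal correlation rho between estimates, from 0 to 0.8; a next trial at two-sided 5% and 80% power; up to six SDSC subscales, so k = 10 to 16. Daytime sleep episodes will yield a rate ratio and are treated as a standardised effect for illustration only.

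**Precision of one estimate.** SE = sqrt(2/n). With 13.5 per arm it is 0.385 (95% CI about +/-0.75); with 22.5 it is 0.298 (about +/-0.58).

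**Largest of ten, all with the same true effect d.** The mean maximum is d + 1.539 x sqrt(1 - rho) x sqrt(2/n), where 1.539 is the expected maximum of ten independent standard normals. A trial sized on an effect m needs 15.70/m² per arm, where 15.70 = 2 x (1.960 + 0.842)². Its real power at d with N per arm is Phi(d x sqrt(N/2) - 1.96). For d = 0.2:

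| Pilot n per arm | rho | Mean largest | Next trial, per arm | Real power |
|---|---|---|---|---|
| 15 | 0 | 0.2 + 1.539 x 0.365 = 0.76 | 28 | 11% |
| 15 | 0.5 | 0.60 | 44 | 15% |
| 15 | 0.8 | 0.45 | 78 | 24% |
| 25 | 0 | 0.2 + 1.539 x 0.283 = 0.64 | 39 | 14% |
| 25 | 0.5 | 0.51 | 61 | 20% |
| 25 | 0.8 | 0.40 | 101 | 30% |

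The true effect of 0.2 needs 15.70/0.04, or 393 per arm. With no effect at all (d = 0) and rho from 0 to 0.5, the largest of ten still averages 0.56-0.40 at 15 per arm and 0.44-0.31 at 25.

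**True effects that differ.** These are simulations with 90% retained, k = 10 or 16 and rho 0.3 to 0.8. The next trial is sized on the largest estimate, and power is taken at the true effect of the phenotype selected. Median real power:

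- three phenotypes at 0.5, the rest at 0 or 0.2: 22-62% (the lowest value is 28% with ten outcomes)
- three at 0.8, the rest at 0.2: 50-69%
- one at 0.8, the rest at 0.2: 40-81%

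**One pre-chosen outcome, d = 0.3, 90% retained.** Median real power is about 51% with 30 enrolled and 61% with 50. These medians cover only pilots whose estimate is positive and large enough to size a trial on. A hand check with a cut-off of 0.05 and 13.5 per arm shows the effect of that condition. The share excluded is Phi((0.05 - 0.3)/0.385) = 26%. The median of the rest is 0.3 + 0.385 x 0.329 = 0.427, which gives 15.70/0.427², about 86 per arm, and power of about 50%. Going ahead only after an encouraging pilot is itself a form of selection.

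**The case against.** A reader might infer that the plan will carry the single largest effect forward. The documents do not say so. The sentence refers to results in the plural, and a focus on magnitude can mean simply that estimates are preferred to p-values. This objection stands: the defect is the missing safeguard, not a declared rule to take the maximum.

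A reader might also infer that the next trial is bound to be badly under-sized. That does not follow. The lowest power figures assume equal true effects, so that ranking is pure noise, whereas the stated aim supposes that some phenotypes respond more than others. Several actigraphy measures overlap by construction, so correlation may be high. Under either condition the loss is milder, and in the most favourable case run there is none.

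Nor does the calculation show that the wrong phenotype would be targeted. With equal true effects, no target is wrong.

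The plan does acknowledge low power and multiple comparisons, SDSC total remains available, and a later trial will have its own protocol. All of this is true and limits the consequence. But none of it governs the sentence at issue, which draws effect sizes from the secondary analyses and not from SDSC total.

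**Conclusion.** The point holds in conditional form. The plan judges at least ten outcomes by observed size in 30-50 children and commits to using the same raw results as effect sizes, with no allowance for selection or imprecision. If a best-looking phenotype is used, its effect is biased upward and the next trial would probably be under-powered.

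The extent is uncertain because the true effects, the correlations and the number of SDSC subscales are not given. The scenarios run from about 11% real power to about the nominal 80%, and most fall well short. Not all of the shortfall comes from choosing among phenotypes: the single-outcome case shows that imprecision, combined with acting only on a positive estimate, is enough to cause it. The samples may also be smaller than assumed for actigraphy, since sections 7 and 11a let families withdraw from that part.

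This pilot's feasibility and acceptability results are unaffected. The change should be made because producing design inputs is part of the trial's purpose.

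**What to change.** Replace the last sentence of the secondary-outcomes paragraph in section 8 so that it says:

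- every phenotype effect is reported with a 95% CI and labelled hypothesis-generating;
- the future trial is sized on a clinically important difference set in advance for its chosen outcome, with the SD and retention taken from this pilot;
- if a pilot effect informs sizing at all, it is an estimate shrunken across all the phenotypes examined, not the raw value of a selected one.

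A lower confidence limit is not a workable substitute. The lower 80% limit for an observed effect of 0.5 is 0.5 - 1.28 x 0.365 = 0.03 at 15 per arm and 0.5 - 1.28 x 0.283 = 0.14 at 25. For an observed 0.2 it is negative at both sizes.

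The cost is a wording change and routine output, with no effect on enrolment, conduct or care. The planned next trial will look larger, and an important difference will have to be justified for whichever outcome is chosen.
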